1.1 STUDY INTRODUCTION

Glaucomatous optic neuropathy (GON) is a group of eye disease, characterized by progressive by loss of retinal ganglion cells (RGC) and axonal degeneration with concomitant optic disc cupping, thinning of the retinal nerve fiber layer (RNFL) and clinically detectable early visual field defects.

It represents a leading cause of irreversible visual impairment and blindness worldwide, estimated to affect 111.8 million people worldwide in 2040 (Tham YC et al, 2014). According to National Eye Survey II, glaucoma is the third leading causes of blindness and low vision in Malaysia (Chew et al, 2018).

Glaucoma can be further divided into two main categories, which are open or closed angle glaucoma. It can be subdivided into primary or secondary. Primary open angle glaucoma (POAG) is the most common type of glaucoma and occurs in elderly individuals with an open angle without gonioscopic abnormalities. Juvenile open angle glaucoma (JOAG) affects the younger population age ranging from 3 to 40 years old.

Pro-inflammatory cytokines such as Interleukin-6 have been linked to play an active role in the immunomodulation of the nerve layer, leading to glaucomatous optic neuropathy. Stingless bee honey (Kelulut) was found to have antioxidant, anti-inflammatory and free radical scavenging properties. The beneficiary effects of honey confer protective effects on neurons against oxidative damage as well as reducing the pro-inflammatory cytokine such as Interleukin-6. We believe that this non-invasive study which involves evaluation of honey Kelulut on the mean

serum level of Interleukin-6 and retinal nerve fiber layer thickness will provide a potential supplementary therapy for JOAG.

1.2 STUDY RATIONALE

Juvenile open-angle glaucoma (JOAG) is a rare form of primary open-angle glaucoma that manifests between the ages of 3 and 40. It is often associated with mutations in the myocilin (MYOC) gene, leading to improper drainage of aqueous humor and resulting in elevated intraocular pressure (IOP). This increased IOP can cause optic nerve damage, leading to irreversible vision loss. JOAG typically follows an autosomal dominant inheritance pattern and often requires surgical intervention due to its resistance to medical therapies.

Kelulut honey, produced by stingless bees, has demonstrated significant anti-inflammatory and antioxidant properties, attributed to its high polyphenolic content. These properties suggest potential neuroprotective effects, which could be beneficial in managing neurodegenerative conditions. In view of oxidative stress and inflammation are key factors in the pathogenesis of glaucoma, Kelulut honey may serve as a valuable adjunct to conventional antiglaucoma therapies.

Monitoring serum levels of interleukin-6 (IL-6), peripapillary retinal nerve fiber layer (RNFL) thickness and its effect on dry eye parameters are established methods for evaluating inflammatory status and glaucomatous damage, respectively. The immunomodulatory effects of Kelulut honey could potentially modulate these biomarkers, leading to improved clinical outcomes for JOAG patients. Findings from research into Kelulut honey's therapeutic potential may lead to the development of more effective treatment strategies for JOAG, ultimately enhancing patient quality of life.

JOAG is a progressive condition that can lead to irreversible damage to the optic nerve if not treated promptly. Given its early onset (often in individuals under 40), the risk of significant vision loss over a long period is high if IOP is not controlled. Since JOAG typically affects younger individuals, if left untreated, the cumulative loss of vision can be substantial, potentially affecting the patient's ability to work, drive, and perform daily activities. The psychological burden of losing vision at a young age can be immense, potentially leading to depression and anxiety, especially for those who are still in school or early adulthood. The role of immunomodulation via the usage of Kelulut honey can prevent the disease from progressing to advanced stages where treatment becomes more complex and reduces the need for invasive interventions.

CHAPTER 2: LITERATURE REVIEW

2.1 JUVENILE OPEN ANGLE GLAUCOMA

Juvenile open angle glaucoma (JOAG) is a type of primary open angle glaucoma, where the onset of disease ranges from 3-40 years of age (Elgin U et al, 2014). Genetic factors have been implicated in the pathophysiology of POAG. JOAG is most commonly inherited in an autosomal dominant fashion with incomplete penetrance. This inheritance pattern has been documented in various studies of familial glaucoma cases (Wiggs & Pasquale, 2017).

Among the major genes associated with JOAG includes Myocillin (MYOC), Cytochrome P450 1B1 (CYP1B1), Forkhead Box C1 (FOXC1), Optineurin (OPTN). Myocillin, *MYOC* gene mutations are associated with 2% to 4% of POAG, and this mutation are reported to be higher in JOAG (Fingert JH et al, 2002). The *MYOC* gene is located on chromosome 1q24.3 (Stone et al., 1997). It encodes myocillin, a protein thought to be involved in the regulation of intraocular

pressure (IOP) by modulating aqueous humor outflow through the trabecular meshwork. MYOC mutations account for 10–30% of JOAG cases (Sarfarazi & Stoilov, 2000). Mutation of myocilin results in protein misfolding and accumulation in the trabecular meshwork cells, causing impaired aqueous outflow and increased IOP. MYOC mutations often result in early-onset, aggressive disease and genetic screening for MYOC mutations is recommended in families with a history of JOAG (Wiggs & Pasquale, 2017).

CYP1B1 is located on chromosome 2p22.2 (Kaur, Mandal, & Chakrabarti, 2008). It plays a role in ocular development and metabolism of endogenous compounds. Homozygous or compound heterozygous mutations in CYP1B1 can lead to structural abnormalities in the trabecular meshwork. Higher prevalence are seen in Middle Eastern, Indian, and other consanguineous populations.

Forkhead Box C1 is located on chromosome 6p25 (Wiggs & Pasquale, 2017). It is involved in the regulation of ocular embryogenesis. Mutations are associated with anterior segment dysgenesis and increased risk of JOAG.

Optineurin (OPTN) is located on chromosome 10p13 (Fingert, 2011), a gene responsible in neuroprotection and the regulation of apoptosis in retinal ganglion cells. Some mutations have been linked to both normal-tension glaucoma and JOAG.

While specific genes like MYOC and CYP1B1 have been implicated, JOAG is likely influenced by multiple genetic loci, each contributing a small effect. Genome-Wide Association Studies (GWAS) have identified additional loci associated with glaucoma risk, including regions near TMCO1, CDKN2B-AS1, and SIX6 (Tham et al., 2014). These loci highlight pathways related to trabecular meshwork function, retinal ganglion cell survival, and anterior chamber development.

While comprehensive epidemiological data specific to Malaysia is limited, studies from neighboring countries and regional research provide valuable insights into its prevalence and characteristics. A recent population-based study in South Korea reported that the incidence of JOAG was 5.02 per 100,000 residents and average prevalence of JOAG was 14.17 per 100,000 residents (Baek Su et al, 2024). In a study conducted in Singapore, JOAG accounted for 3.3% of all newly diagnosed glaucomas, with a mean age at diagnosis of 26 ± 9.8 year (Selvan H et al, 2022).

JOAG is distinct from congenital glaucoma which presents with buphthalmos, megalocornea, Haab's striae, and ocular or other systemic developmental anomalies. JOAG is distinguished by its elevation in intraocular pressure with large fluctuations, faster progression and severity of visual field loss compared to adult POAG. Managing JOAG patients is challenging as medical treatment is often inadequate where most patient eventually requires surgical intervention for effective management (Ciociola EC et al 2022). The resulting visual impairment and blindness can significantly impair the patient's quality of life and limit daily living activities.

2.2 IMMUNOMODULATION

Recent studies suggest that immune system and neuroinflammation plays a major contributing factor in the pathogenesis of optic neuropathy in glaucoma (Adornetto A et al, 2019). Adaptive and protective responses of resident or systemic immune cells can support neurons and promote tissue repair mechanisms after injurious insults, however prolonged inflammatory processes can also produce neurotoxic mediators (Tezel G, 2013). In glaucoma, chronic glial activation along with a failure in the regulation of immune response pathways may compromise the immune homeostasis resulting in neurodegeneration and promote secondary injury to neurons. Both

astroglia and microglia resident in the retina and optic nerve (head) profoundly respond in glaucomatous human donor eyes and animal models with glaucoma.

Astroglia (retina and optic nerve astrocytes, and retinal Müller cells) normally preserve tissue homeostasis, maintain synapses, recycle neurotransmitters, deliver neurotrophic factors and metabolites, control blood flow and vascular barriers, and participate neurogenesis. These neurosupportive cells quickly recognize and respond to stress and injury signals as a neuronal defense and recovery mechanism. In glaucomatous optic nerve head, astroglia responses leads to tissue remodeling and glial scarring, creating biomechanical stress on optic nerve axons. Microglia cells normally provide neurotrophic support, and their scavenger and phagocytosing functions promote tissue cleaning and healing. Similar to astroglia cells, its chronic activation leads to injury to optic nerve axons (Barış M, 2019)

Other cells such as myelin-producing oligodendrocytes and blood-borne monocytes are also linked to inflammatory component in glaucoma. Thus, chronic tissue stress, neuron injury, glial and systemic immune responses, and sustained release of neurotoxic mediators may create a vicious cycle that may promote progressing neuron injury. Treatments targeting these neurodestructive outcomes is critical for the survival of neuronal tissue while avoiding neurodegenerative inflammation.

[figure not shown]

Figure 1: Immune regulation in glaucoma. Various pathways, such as pro-inflammatory cytokine signaling (including TNF- α /TNFR signaling), TLR signaling, NF- κ B activation, NLRs and inflammasome assembly, and complement activation are co-players of inflammatory responses in glaucomatous tissues. A failure in the regulation of immune response pathways may shift the physiological equilibrium toward an inflammatory neurodegenerative process.

2.3 INTERLEUKIN-6

IL-6 is a proinflammatory cytokine that plays an important role in mediating inflammation in glaucomatous eye. Retinal ganglion cells (RGC) do not normally regenerate axons after injury, instead undergo apoptotic cell death (Leibinger M et al, 2016). IL-6 is synthesized by injured retinal ganglion cells following elevation of intraocular pressure and transported in an orthograde fashion along the nerve, accumulating at axonal disruption in the optic nerve head (Chidlow G et al, 2012). This results in inflammation and apoptosis of RGC.

While direct studies on serum IL-6 levels in JOAG are lacking, existing research on POAG and NTG suggests a potential association between IL-6 and glaucoma. Studies also suggest that higher serum levels of IL-6 are associated with primary open angle glaucoma and its severity (Huang P et al, 2010, Ulhaq ZS et al, 2021). Another study found that serum IL-6 levels were borderline higher in NTG patients compared to controls, suggesting a potential association between serum IL-6 alterations and glaucoma. (Lin KH et al, 2014).

2.4 RETINAL NERVE FIBER LAYER

The retinal nerve fiber layer (RNFL) contains the non-myelinated axons of the RGCs that form the optic nerve. RNFL thinning reflects the axonal loss within the optic nerve. In normal discs, the RNFL is thicker in the inferior and superior quadrants of the disc, and thinner in the nasal and temporal quadrants of the disc. The mean RNFL thickness for the normal population is $97.3 \pm 9.6 \mu\text{m}$ (Alasil T et al, 2013) whereas the rate of normal age-related retinal thinning is $-0.54 \pm 0.23 \mu\text{m/year}$ (Wu Z et al, 2017).

Structural damage almost always precedes functional damage. Damage to the RNFL precedes observable changes in the optic nerve head and significant RNFL loss can occur before reproducible functional loss can be demonstrated (Choplin NT et al, 2015). Using light from a low coherence source, optical coherence tomography (OCT) precisely measures the RNFL surrounding the optic nerve head (peripapillary RNFL). A normative database of the RNFL thickness has been obtained to identify and monitor the changes during follow up.

RNFL thinning often precedes visual field loss, which is why monitoring RNFL changes is so important. In the early stages, patients with JOAG may not notice significant changes in their vision, but OCT can detect the thinning of the RNFL long before visual field defects appear. The rate at which the RNFL thins over time is a critical factor in determining the progression of JOAG. A rapid rate of RNFL loss may indicate that the glaucoma is progressing more quickly, and treatment may need to be adjusted to prevent further damage.

2.5 STINGLESS BEE HONEY (KELULUT)

With the advent of recent scientific approaches, honey is being widely recognized as treatment adjuvant for many diseases owing to its anti-oxidant, anti-inflammatory, anti-microbial, anti-cancer and wound healing properties (Al-Hatamleh MA et al, 2020). Honey possesses a wide variety of bioactive components, approximately 200 different compounds. Its beneficiary effects are attributed particularly by flavonoids and polyphenols, which protect neurons against oxidative damage and neurotoxicity, improve neuronal function and enhance regeneration (Iftikhar A et al, 2022).

Stingless bee honey (Kelulut) is a tropical rainforest honey produced by tropical Meliponini bee species. It is postulated that Kelulut has better antioxidant, anti-inflammatory and free radical

scavenging properties than other local honey, owing to the higher contents of phenolic acid and flavonoid substance (Kek SP et al, 2017).

Recent evidence indicates stingless bee honey decreased the IL-6 secretion by macrophages after lipopolysaccharide (LPS) stimulation, reaching a reduction of 43.9% (Biluca FC et al, 2020). In support of these findings, stingless bee honey decreased the circulating levels IL-6 in different tissues of lipopolysaccharide-induced rats (Ranneh Y et al, 2021). Trigona honey (Madu Kelulut) significantly reduced the mean IL-6 level among ventilated pneumonia patient in intensive care unit compared to control group (p value < 0.001). The reduction was observed between Day 0 and Day 6 of treatment (Omar SC et al, 2020). In Malaysia, the domestic cultivation of Kelulut honey on a large scale is made possible in a controlled farm environment, hence adding to the cost effectiveness (Mustafa MZ et al, 2018). The majority of honey's health-promoting qualities can only be obtained by applying large dosages of the substance, between 50 and 80 g per intake (Bogdanov S et al, 2018).

Another study evaluated the effect of honey on macular thickness, retinal nerve fiber layer thickness and optic nerve head parameters in post-menopausal women with honey cocktail of 20g/day for 3 months showed significant increase in the mean change of global RNFL thickness in honey cocktail group at three months post honey cocktail supplement, with p value of < 0.001 (Sivagurunathan et al, 2019).

The article titled "Therapeutic Potential of Honey and Propolis on Ocular Disease" by Norhashima et al published in *Pharmaceuticals* in November 2022, provides a comprehensive review of the pharmacological properties of honey and propolis in the context of ocular health. A clinical study Jung Won Park et al. highlights the neuroprotective effects of Brazilian Green Propolis (BGP) on retinal ganglion cells (RGCs) in an ischemic mouse retina model. Results suggest that BGP has a neuroprotective effect on RGCs through the upregulation of histone acetylation, downregulation of apoptotic stimuli, and suppression of NF-κB mediated

inflammatory pathway in ischemic retina. Kelulut honey which also known for its potent anti-inflammatory and antioxidant properties, might have similar effects on the retina. This study is proposed to evaluate whether *Kelulut* honey reduces IL-6 levels and protects against neurodegeneration in JOAG patients, paralleling the effects seen with propolis in the mouse model.

CHAPTER 3: STUDY OBJECTIVES, RESEARCH QUESTIONS, RESEARCH HYPOTHESIS

3.1. STUDY OBJECTIVES

3.1.1. GENERAL OBJECTIVES

To evaluate the effects of supplementary therapy of stingless bee honey (Kelulut) on the mean serum level of Interleukin-6, retinal nerve fiber layer thickness and dry eye disease parameters in patients with JOAG.

3.1.2. SPECIFIC OBJECTIVES

1. To compare the mean serum level of Interleukin-6 in patients with JOAG with and without honey Kelulut consumption for 3 months.
2. To compare the mean retinal nerve fiber layer thickness in patients with JOAG with and without honey Kelulut consumption for 3 months.

3. To compare the tear break-up time (TBUT) and Schirmer test in patients with JOAG with and without honey Kelulut consumption for 3 months.

4. To compare the level of glycated hemoglobin (HbA1c) level in patients with JOAG with and without honey Kelulut consumption for 3 months.

3.2. RESEARCH QUESTIONS

- 3.2.1. Does the mean serum level of interleukin-6 differs with and without

consumption of honey Kelulut for 3 months among JOAG patients?

3.2.2. Does the mean thickness of retinal nerve fiber layer increases with consumption of honey Kelulut for 3 months among patients with JOAG?

3.2.3. Does the tear break-up time (TBUT) and Schirmer test increases with consumption of honey Kelulut for 3 months among patients with JOAG?

3.2.4. Does the level of glycated hemoglobin (HbA1c) increases with consumption of honey Kelulut for 3 months among patients with JOAG?

3.2. RESEARCH HYPOTHESIS

3.2.1. The mean serum level of Interleukin-6 reduces after consumption of honey Kelulut for 3 months among patients with JOAG.

3.2.2. The mean thickness of retinal nerve fiber layer increases after consumption of Honey Kelulut for 3 months among patients with JOAG.

3.2.3 The tear break-up time (TBUT) and Schirmer test increases after consumption of honey Kelulut for 3 months among patients with JOAG.

3.2.4 The level of glycated hemoglobin (HbA1c) does not increase with the consumption of honey Kelulut for 3 months among patients with JOAG.

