3.3.4 For level of glycated hemoglobin

Null Hypothesis:

There is no significance difference in the level of glycated hemoglobin level after consumption of honey Kelulut for 3 months among patients with juvenile-onset open-angle glaucoma (JOAG).

CHAPTER 4: METHODOLOGY

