4.4. SAMPLE SIZE

Sample size calculation

GPower 3.1.9.7 software was used to calculate the sample size.

The power of the study will be set at 80% with a significance level of 5%.

For the sample size calculation was statistical data used was repeated measures ANOVA within and within between.

The largest sample size was 24.

To account for the attrition rate, 20% was added, which gives a total estimated minimum sample size of 30 per group.

Total sample size: 60 (30 per group)

Objective 1:

To compare the mean serum level of Interleukin-6 before and after consumption of honey Kelulut for 3 months among patients with JOAG.

Calculated sample size: 24

By the addition of 20% drop outs, the sample size that needs to be collected for each group is 30 subjects

Total sample size: 60

Objective 2:

To compare the mean RNFL thickness before and after consumption of honey Kelulut for 3 months among patients with JOAG.

Calculated sample size: 24

By the addition of 20% drop outs, the sample size that needs to be collected for each group is 27 subjects.

Total sample size: 60

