4.10.6. DATA COLLECTION AND ANALYSIS

Data recorded in data collection sheet transferred into electronic data and analyzed using Statistical Package for Social Sciences (SPSS), the latest version. The mean serum IL-6 and mean RNFL thickness of both groups will be analyzed using ANOVA repeated measures; within factors and within-between factors. All the p-value of less than 0.05 was considered statistically significant.

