5.1 DEMOGRAPHIC DATA

Variables	Honey group (n = 43)	Control group (n = 43)	p value
Age (years)			
Sex			
Male, n (%)			
Female, n (%)			
Race			
Malay, n (%)			
Chinese, n (%)			
Indian, n (%)			
Others, n (%)			
BCVA (Log MAR)			
Duration of JOAG (years)			
Number of topical antiglaucoma medications			
Received surgical intervention for IOP control			

5.2 COMPARISON OF MEAN SERUM LEVEL OF IL-6 PRE AND POST 3 MONTHS OF HONEY (KELULUT) TREATMENT AMONG PATIENTS WITH JOAG

Comparison of mean serum level of IL-6 pre and post 3 months of honey (Kelulut) treatment among patients with JOAG

Mean serum IL-6 level value	Group	Mean diff (95% CI)	p
Time			
Baseline	Honey No honey		
3 months' post treatment	Honey No honey		

5.3 COMPARISON OF MEAN RETINAL NERVE FIBER LAYER THICKNESS PRE AND POST 3 MONTHS OF HONEY (KELULUT) TREATMENT AMONG PATIENTS WITH JOAG

RNFL thickness	Group	Mean diff (95% CI)	p value
Time			
Baseline	Honey No honey		
3 months' post treatment	Honey No honey		

5.4 COMPARISON OF DRY EYE DISEASE PARAMETERS PRE AND POST 3 MONTHS OF HONEY (KELULUT) TREATMENT AMONG PATIENTS WITH JOAG

[figure not shown]
Comparison of TBUT	Group	Mean diff (95% CI)	p value
<hr/>			
Time			
Baseline	Honey No honey		
3 months' post treatment	Honey No honey		

Comparison of Schirmer test	Group	Mean diff (95% CI)	p value
<hr/>			
Time			
Baseline	Honey No honey		
3 months' post treatment	Honey No honey		

5.5 COMPARISON OF LEVEL OF GLYCATED HEMOGLOBIN PRE AND POST 3 MONTHS OF HONEY (KELULUT) TREATMENT AMONG PATIENTS WITH JOAG

HbA1c	Group	Mean diff (95% CI)	p value
<hr/>			
Time			
Baseline	Honey No honey		
3 months' post treatment	Honey No honey		

CHAPTER 6: FLOW CHART

CHAPTER 7: GANTT CHART

Year	2024	2024-2025		2025-2026		2026
Months	Jan-May	Jun-Nov	Dec-May	Jun-Nov	Dec-May	Jun
Proposal preparation and ethical approval			→			
Data collection					→	
Data analysis/interpretation					→	
Report writing					→	
Submission of research book						→

CHAPTER 8: MILESTONE

Data	Expected achievement
Jan 2024 – November 2024	Proposal presentation (Department of Ophthalmology USM) Jawatankuasa Etika Penyelidikan Manusia (JEPEM) USM presentation NMRR application
December 2024-February 2025	JEPEM and NMRR approval
March 2025 – May 2025	30% of data collection
June 2025 – November 2025	80% of data collection 30% of report writing
December 2025 – May 2026	100% data collection 100% of data analysis 100% of report writing
June 2026	Submission of research book

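### The HbA1c research hypothesis (no increase) contains its own null (no difference), so unless HbA1c falls significantly only a non-significant result can support it

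*Protocol*

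**What the plan says.** HbA1c is the fourth specific objective in section 3.1.2: "To compare the level of glycated hemoglobin (HbA1c) level in patients with JOAG with and without honey Kelulut consumption for 3 months". The matching item under Research Questions asks whether HbA1c goes up. The research hypothesis, item 3.2.4, answers that "The level of glycated hemoglobin (HbA1c) does not increase with the consumption of honey Kelulut for 3 months among patients with JOAG". Its null, section 3.3.4, reads "There is no significance difference in the level of glycated hemoglobin level after consumption of honey Kelulut for 3 months".

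The other outcomes are framed differently. Item 3.2.1, for example, asserts a change: "The mean serum level of Interleukin-6 reduces after consumption of honey Kelulut for 3 months among patients with JOAG". Items 3.2.2 and 3.2.3 likewise assert increases in RNFL thickness and in the two tear measures.

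Section 4.10.6 gives one decision criterion for everything: "All the p-value of less than 0.05 was considered statistically significant". It does not say whether tests are one- or two-sided. The HbA1c table shell in section 5.5 has columns for a mean difference with 95% CI and a p value, but nothing links the interval to hypothesis 3.2.4.

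**The concern.** A significance test can reject a null; it cannot establish one. That works for items 3.2.1 to 3.2.3, where rejecting the null in the stated direction supports the hypothesis. For HbA1c the hypothesis and the null are on the same side. Rejecting 3.3.4 because HbA1c rose refutes 3.2.4, and rejecting it because HbA1c fell supports 3.2.4. In every other case the null stands, and the wording invites the reader to take that as confirmation.

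This rewards imprecision: fewer patients, more missing data or a noisier assay all make a non-significant result more likely. The honey is a daily product made up mainly of sugars (sections 4.7 and 4.8), so HbA1c works here as a safety check. A conclusion of no increase that rests only on a non-significant p value would reassure without evidence.

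**Working it through.** **Logic.** Let δ be the true effect of honey on HbA1c, positive for a rise. For the tear measures, δ stands for each of TBUT and Schirmer.

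| Outcome | Research hypothesis | Null | Null inside hypothesis? |
|---|---|---|---|
| IL-6 (3.2.1 / 3.3.1) | δ < 0 | δ = 0 | No |
| RNFL (3.2.2 / 3.3.2) | δ > 0 | δ = 0 | No |
| TBUT, Schirmer (3.2.3 / 3.3.3) | δ > 0 | δ = 0 | No |
| HbA1c (3.2.4 / 3.3.4) | δ ≤ 0 | δ = 0 | **Yes** |

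A one-sided test does not rescue the HbA1c pair. Tested for a rise, the null is δ ≤ 0, which is 3.2.4 itself. Tested for a fall, the null is δ ≥ 0, and only a significant fall supports 3.2.4.

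**Stated figures.** The protocol gives no sample size, power, SD or limit for HbA1c, so there is no HbA1c figure to reproduce. The nearest check is section 4.4: 24 inflated for 20% attrition is 24 / (1 − 0.20) = 30, which matches the 30 per group stated there. The 24 is read as evaluable patients per group.

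**Illustration of size.** From the protocol: 24 per arm (evaluable) or 30 per arm (no attrition), and a 5% level. Assumed, because the protocol is silent: SD of HbA1c change 0.2, 0.3 or 0.4 percentage points; true rise 0.2 points; two-sided test; independent patients.

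Standard error = SD × √(2/n); degrees of freedom = 2n − 2; half-width of the 95% CI = t(0.975) × SE. The probability of p > 0.05 comes from the noncentral t distribution with noncentrality 0.2 / SE. For n = 24 and SD = 0.3: SE = 0.3 × √(2/24) = 0.087, noncentrality = 2.31, t(0.975, 46) = 2.013, half-width = 0.174, probability of non-significance = 0.382.

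| n per arm | SD of change | SE | 95% CI half-width | Non-significant despite a true rise of 0.2 |
|---|---|---|---|---|
| 24 | 0.2 | 0.058 | 0.12 | 8% |
| 24 | 0.3 | 0.087 | 0.17 | 38% |
| 24 | 0.4 | 0.115 | 0.23 | 60% |
| 30 | 0.2 | 0.052 | 0.10 | 3% |
| 30 | 0.3 | 0.077 | 0.16 | 28% |
| 30 | 0.4 | 0.103 | 0.21 | 52% |

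**Other readings of the test**, for SD 0.2 / 0.3 / 0.4:
- Before-after in the honey arm only, SE = SD/√n: 0.3 / 12 / 35% with 24 patients; below 0.1 / 6 / 25% with 30.
- Between groups, one-sided 5% test for a rise: 4 / 26 / 48% with 24 per arm; 1 / 18 / 39% with 30.

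**The case against.** The strongest reply is that this is an ordinary harm check. The research question asks whether HbA1c increases, the null is no difference, and a significant rise is the warning signal. On that reading 3.2.4 merely records the expected answer, and the protocol nowhere says that a non-significant result will count as proof. The interval planned in section 5.5 would also temper over-reading of a bare p value, and the HbA1c method, any margin and the rule for interpretation could properly sit in a statistical analysis plan that is not shown.

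Part of this stands. The protocol does not commit the error outright; it leaves no other route to support short of a fall. The absence of a margin or a named HbA1c analysis is not held against the protocol here. It is also fair that the percentages rest on assumed inputs and run from negligible to more than half.

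The harm-check reading does not cure the pair, however. Item 3.2.4 is labelled a research hypothesis alongside three that are to be supported by rejecting their nulls, and on that reading a non-significant rise would still be its confirmation. An interval with no stated link to the hypothesis does not change this. A separate analysis plan could add a rule, but the faulty pair would remain in the protocol.

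**Conclusion.** The concern holds, as a minor point. The fault is in the wording of 3.2.4 and 3.3.4 and depends on no numerical assumption.

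The consequence does depend on assumptions. For a true rise of 0.2 points and the SDs tried, between 3% and 60% of trials would show no significant difference between the groups on a two-sided test. The range extends lower if the test is one-sided or before-after. All these figures treat patients as independent. Section 4.6 allocates whole centres, two per arm, which would lower precision further; that is a separate issue.

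The reach is limited. The general objective in section 3.1.1 covers effects "on the mean serum level of Interleukin-6, retinal nerve fiber layer thickness and dry eye disease parameters in patients with JOAG" and does not name HbA1c. The total of 60 in section 4.4 is worked out for IL-6 and RNFL only.

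**What to change.** 1. Reword 3.2.4 and 3.3.4 around the honey minus no-honey difference in HbA1c change, which is the comparison that objective 4 calls for.
2. Report that mean difference with the 95% CI already planned in section 5.5, computed so that it respects allocation by centre.
3. Add one rule for interpretation: draw no statement of no increase from a non-significant p value; say which rises the interval excludes and which it does not.
4. Only if the sponsor wants to claim no increase: fix and justify a margin before enrolment, and require the upper 95% limit to lie below it. The margin is the sponsor's judgement, and none is proposed here.

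Steps 1 to 3 cost two reworded sentences and one added rule, with no extra patients or measurements. The price is that the reassuring conclusion becomes harder to reach.

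Step 4 may strain the planned size. With a margin of 0.2 points used purely for illustration, no true rise, independent patients and SDs of 0.2 / 0.3 / 0.4, the claim would be reached in 92 / 62 / 40% of trials with 24 per arm and 97 / 72 / 48% with 30, and less often once allocation by centre is respected.
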